- g. Vital sign measurements include systolic/diastolic blood pressure and HR. Pulse oximetry should be performed with vital signs. Respiratory rate and body temperature should also be measured pre dose and at 2, 4, 6, and 8 hours post dose Cycle 1, Day 1 and pre dose Cycle 2, Day 1. Vital signs should be measured in the resting state. This procedure should not be conducted during the supine position for ECG measurement.
- h. Beginning with Cycle 1, Day 1, DS 1205c should be administered following a meal, with 240 mL of water. On the morning of Endpoint ECG days, breakfast should be started 30 minutes prior to dosing and should be completed within approximately 20 minutes. For all other dosings, it is recommended that meals (breakfast or dinner) be completed within approximately 30 minutes; DS 1205c should be taken immediately after meal completion. Doses of DS 1205c should be taken approximately 12 hours apart. Gefitinib is co administered with the morning dose of DS 1205c. The Schedule of Events table above specifies only those meals and doses to be administered in clinic and does not explicitly list the meals and doses to be taken by the subject at home.
- i. Meals administered in the clinic on Days 1, 4, 8, and 15 of Cycle 1 and Days 1 and 2 of Cycle 2 should be time matched to, and contain similar contents as meals administered on Day 1 of Cycle 0. Lunch can be given approximately 4 hours after dosing.
- j. All PK blood draws should be performed as close as possible to the scheduled time, with windows of 2 hours (for pre dose), \pm 15 minutes (for hours 1 to 10 post dose), and \pm 2 hours (for 24 hours post dose). When an ECG is performed at the same time point, the PK specimen should be taken immediately after completion of the ECG. If both DS 1205a and gefitinib are measured at the same time point, separate 3 mL samples should be obtained. Refer to the Laboratory Manual for instructions about collection, processing, and shipping of samples.
- k. To be obtained/Performed pre dose and at 2, 4, 6, 8, and 24 hours post dose.
- l. Obtain eight 5 mL samples for exploratory pharmacodynamic biomarkers (cfDNA and exosomes). As a general rule, blood collection should be conducted after ECG measurement. Refer to the Laboratory Manual for instructions for collection, processing, and shipping of samples.
- m. Obtain three 3 mL samples for pharmacodynamic biomarkers (osteopontin, IL 8, SAXL) pre dose as indicated. As a general rule, blood collection should be conducted after ECG measurement. Refer to the Laboratory Manual for instructions for collection, processing, and shipping of samples.
- n. A bone scan (99m technetium polyphosphonate scintigraphy, whole body bone MRI, or 18F NaF) to assess bone metastases should be performed every 24 weeks (within that 24th week) from C1D1, or sooner if clinically indicated. In subjects whose body CT/MRI scans indicate CR has been achieved, a bone scan should be required at confirmation of CR to exclude new bone metastases. Lesions detected on bone scans must be followed with cross sectional imaging.
- o. The same methodology (CT or MRI) and scan acquisition techniques (including use or nonuse of IV contrast) as were used for the screening assessments should be used throughout the study for all assessments for each subject unless prior approval is obtained from the Sponsor. Unscheduled tumor assessments may be conducted if progression is suspected. Tumor assessments should not be delayed by dose interruptions; they are timed relative to Cycle 1, Day 1. Tumor assessments should be performed per RECIST version 1.1.
- p. Investigator determined tumor assessments of the chest, abdomen, and pelvis and other areas where scans were performed at screening or newly suspected disease should be performed every 6 weeks (\pm 7 days) from Cycle 1, Day 1 for the first 24 weeks then every 12 weeks (\pm 7 days) thereafter. Objective responses must be confirmed at least 4 weeks later (eg, generally at the next tumor assessment time point). Perform CT or MRI of the brain in subjects with baseline brain metastases or if clinically indicated, and within a target of 1 week after a subject achieves a CR.
- q. Perform radiographic tumor assessments (CT/MRI) of the chest, abdomen and pelvis and all sites of disease, as per RECIST version 1.1. If the previous scan was performed within the last 6 weeks, this assessment does not need to be performed at the EOT visit.
- r. Ophthalmologic assessments (visual acuity, slit lamp examination, fundoscopy, and tonometry) should be performed on Day 1 of Cycle 2 (7 days), on Day 1 of Cycle 4 (7 days) and every 4 cycles (7 days) thereafter, and at EOT(7 days). Investigators must ensure results of ophthalmologic assessments are available for review prior to dosing on corresponding cycle visits.
- s. ECHO or MUGA should be performed on Cycle 2, Day 1 (7 days); Cycle 4, Day 1 (7 days), and on Day 1 of every 4 cycles (7 days) thereafter, and at EOT (7 days). The same test must be used for the subject throughout the study. Investigators must ensure results of ECHO/MUGA are available for review prior to dosing on corresponding cycle visits.

[figure not shown]
- t. On study biopsy is optional on Cycle 1, Day 15 (+7 days). Consent for this biopsy should be documented in the tissue consent portion of the appropriate ICF. Tumor biopsy may be obtained from primary tumor or metastatic site.
- u. EOT tumor biopsy is optional. Tumor biopsy should be obtained from primary tumor or metastatic site, preferably from a site of recent radiographic progression, within 30 days of the last dose of study drug, and prior to starting any new anticancer treatment.
- v. All clinical AEs occurring after the subject signs the Appropriate ICF and up to F/U visit (30 days [+7 days] after the final dose of study treatment, or before starting new anticancer treatment, whichever comes first) should be reported.

CCI

[figure not shown]
CCI

CCI

CCI

CCI

CCI

7. EFFICACY ASSESSMENTS

7.1. Assessments for Efficacy Endpoint(s)

7.1.1. Efficacy Endpoint(s)

Efficacy assessments will be determined at Screening and by follow-up imaging using RECIST version 1.1 (Section 17.2). Tumor assessments should be conducted every 6 weeks (± 7 days) from Cycle 1, Day 1 for the first 24 weeks then every 12 weeks (± 7 days) thereafter, as indicated in the Schedule of Events (Table 6.2, Table 6.3), until radiological progression or until the subject permanently discontinues treatment. The schedule of efficacy assessments is determined relative to Cycle 1, Day 1 and will not be altered by interruptions in treatment. The antitumor activity endpoints will include percentage change in size of target lesion(s), ORR, DOR, DCR, PFS, and OS. ORR is defined as the sum of CR and PR rates. CR includes both confirmed CR (as described in Section 6.1.3.5 and Section 6.2.2.6) and unconfirmed CR. DOR is measured from the time of first CR or first PR until the first date of PD. TTR is measured from the date of first dose of DS-1205c to first objective response (CR or PR). DCR is the sum of CR rate, PR rate, and SD rate. PFS is defined as the time from the date of first dose of DS-1205c to the earliest date of the first objective documentation of radiographic disease progression per RECIST Version 1.1 or death due to any cause. OS is defined as from the date of first dose of DS-1205c to death due to any cause.

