5.6. Subject Withdrawal/Discontinuation

5.6.1. Reasons for Withdrawal/Discontinuation

Subjects may be withdrawn from the study for the following reasons:

- PD per criteria set forth in RECIST version 1.1 (Section 17.2)

- Clinical progression (definitive clinical signs of disease progression, but a recent radiographic assessment did not meet the criteria for PD according to RECIST version 1.1)
- AE
- Withdrawal of consent by subject
- Investigator discretion
- Death
- Pregnancy
- Study terminated by Sponsor
- Lost to follow-up
- Other, specify

If the subject is withdrawn due to an AE, the Investigator will follow the subject until the AE has resolved or stabilized. All subjects who are withdrawn from study treatment should complete protocol-specified withdrawal procedures (Section [5.6.2](#)).

Record the reason for treatment discontinuation for any subject who discontinues study treatment for any reason.

Discontinued subjects will be followed for survival, either through direct contacts or by collecting public records (eg, death certificates) as allowed by local laws.

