6.1.3.8. End-of-Treatment (EOT) Visit (Dose Escalation)

This visit occurs within 7 days after the final dose of study treatment, or before starting new anticancer treatment, whichever comes first.

The following procedures should be obtained/Performed per the Schedule of Events, Dose Escalation (Cycle 1 and Beyond) (Table 6.2):

- Vital signs (systolic and diastolic blood pressure, HR) and SpO₂ (pulse oximetry), pre-dose. Vital signs should be measured in the resting state (Section 9.9). This procedure should not be conducted during the supine position for ECG measurement.

- Safety ECGs: 12-lead ECG recordings should be printed for on-site safety assessment by the Investigator. Subjects should be resting supine for at least 10 minutes prior to and 5 minutes after ECG extraction.
- Obtain blood for hematology and blood chemistry. As a general rule, this procedure should be conducted after ECG measurement. If this procedure needs to be done before ECG measurement, investigators should contact Sponsor for guidance in scheduling of these procedures.
- Obtain blood for coagulation (Section 9.8). As a general rule, this procedure should be conducted after ECG measurement. If this procedure needs to be done before ECG measurement, investigators should contact Sponsor for guidance in scheduling of these procedures.
- Obtain urine for urinalysis.
- Obtain a urine sample for pregnancy testing in women of child-bearing potential.
- Obtain blood sample for Exploratory Blood cfDNA. As a general rule, this procedure should be conducted after ECG measurement.
- Obtain blood sample for Exploratory Blood Biomarker. As a general rule, this procedure should be conducted after ECG measurement.
- Perform a complete physical examination, including weight (Section 9.11), and assess and record the functional status using the ECOG PS scale (Appendix 17.4).
- Perform radiographic tumor assessments (CT/MRI) of the chest, abdomen and pelvis and all sites of disease, as per RECIST version 1.1 (Section 17.2). If the previous scan was obtained within the last 6 weeks, this assessment does not need to be performed at the EOT visit.
- Ophthalmologic evaluation should be performed. Assessments should include visual acuity testing, slit lamp examination, fundoscopy, and tonometry (Section 9.12). Assessments may be performed with a window of up to 7 days prior.

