17.2.2.4.4. Special Notes on Response Assessment

When nodal disease is included in the sum of target lesions and the nodes decrease to “normal” size (< 10 mm), they may still have a measurement reported on scans. This measurement should be recorded even though the nodes are normal in order not to overstate progression should it be based on increase in size of the nodes. As noted earlier, this means that subjects with CR may not have a total sum of “zero” on the eCRF.

Subjects with a global deterioration of health status requiring discontinuation of treatment without objective evidence of disease progression at that time should be reported as “symptomatic deterioration.” Every effort should be made to document objective progression even after discontinuation of treatment. Symptomatic deterioration is not a descriptor of an

objective response: it is a reason for stopping study therapy. The objective response status of such subjects is to be determined by evaluation of target and non-target disease.

For equivocal findings of progression (eg, very small and uncertain new lesions; cystic changes or necrosis in existing lesions), treatment may continue until the next scheduled assessment. If at the next scheduled assessment, progression is confirmed, the date of progression should be the earlier date when progression was suspected.

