17.2.2.4.5. Frequency of Tumor Re-evaluation

In this study, tumor measurement will be conducted every 6 weeks in the first 24 weeks after Day 1 of Cycle 1 and thereafter every 12 weeks while the subject remains on study until progression of disease, withdrawal of consent, death, or loss to F/U. Scan dates should not be adjusted or rescheduled due to dose interruption of any type.

Baseline tumor assessments must be performed within 22 days of the first dose of study drug administration.

All efforts should be made to ensure consistency between the baseline measurements and all subsequent measurements in reference to utilization of scanning method, equipment, technique (including slice thickness and field of view), and radiographic interpreter.

The radiographic evaluation must include CT or MRI scanning of the brain, chest, abdomen, and pelvis at screening period. Any additional suspected sites of disease should also be imaged. Every effort should be made to use the same assessment modality for all assessments for each subject. However, if there is no brain metastasis at the time of screening, CT or MRI should only be done when symptoms associated with brain metastasis occur during study period. If no clinical symptoms are observed, brain CT or MRI is not mandatory during study period. All evaluations should meet the standard of care for imaging of lesions in the respective organ(s) and should conform to the image acquisition guidelines according to institutional standards.

All target and non-target sites are evaluated at each time point of tumor assessment.

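### Section 7.1.1 ends tumor scans when treatment stops, while Appendix 17.2 asks for progression to be documented afterwards; following 7.1.1 biases PFS and DOR upward by an amount the documents do not fix

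*Combined protocol and SAP*

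**What the plan says.** Two parts of the protocol say when scanning ends. Section 7.1.1 runs the 6-weekly, later 12-weekly, schedule "until radiological progression or until the subject permanently discontinues treatment". Section 17.2.2.4.5 runs the same schedule "while the subject remains on study until progression of disease, withdrawal of consent, death, or loss to F/U". Section 17.2.2.4.4, on subjects taken off treatment for deteriorating health without objective progression, adds: "Every effort should be made to document objective progression even after discontinuation of treatment".

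Section 5.6.1 lists clinical progression as a withdrawal reason, described as "definitive clinical signs of disease progression, but a recent radiographic assessment did not meet the criteria for PD according to RECIST version 1.1".

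The end-of-treatment visit includes a scan, with a waiver: "If the previous scan was obtained within the last 6 weeks, this assessment does not need to be performed at the EOT visit" (Section 6.1.3.8; Table 6.2 note q agrees). After that, Section 6.1.3.10 and Table 6.2 collect survival and subsequent therapy every 3 months and list no imaging.

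The PFS event in Section 7.1.1 is "the first objective documentation of radiographic disease progression per RECIST Version 1.1 or death due to any cause". For DOR, "DOR is measured from the time of first CR or first PR until the first date of PD". Section 11.4 summarizes both by Kaplan-Meier and leaves the censoring rules for time-to-event endpoints to the SAP.

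**The concern.** A subject who stops because the disease is clearly worsening, but whose last scan fell short of RECIST PD, is likely to progress soon. If scanning ends with treatment, that progression is never recorded. Kaplan-Meier assumes that censored subjects have the same outlook as those still followed, and these subjects have a worse one. PFS and DOR then look longer than they are.

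The trial has no control arm, so a reader can only set these endpoints beside outside results such as those in Section 1.2.1, where a few points can matter. Sites following 7.1.1 and sites following Appendix 17.2 would also collect different data. A progression that was never imaged cannot be recovered later by SAP wording.

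**Working it through.** **Reading the rules together for one subject.** Take a subject who stops for clinical progression during the 6-weekly phase.

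1. Section 7.1.1: scheduled scans end at discontinuation.
2. Section 6.1.3.8: the end-of-treatment scan is waived if a scan was done within 6 weeks. On a 6-weekly schedule that is the usual case. In the 12-weekly phase the scan is more often required.
3. Section 6.1.3.10: later contacts collect survival and new therapy only.
4. DOR: PD is the only event, so none can be observed.
5. PFS: either censored at or near the last scan, or counted at a later death. Both give a longer time than the missed PD would have.
6. Section 17.2.2.4.4 would have had this subject's progression documented.

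**Size.** The documents give no PFS or DOR figure, no rate of stopping for clinical progression and no censoring rule, so there is nothing to reproduce. What follows is illustration.

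Inputs: scans at weeks 6, 12, 18 and 24, then every 12 weeks (Section 17.2.2.4.5). Assumed: exponential time to PD with median 16 weeks; a share of 10-40% stopping at a uniformly distributed time in the 6 weeks before PD. In one version none of these subjects has a scan showing PD at stopping, and all are censored at their last scan. In the other, half have such a scan and count as events on that date. Deaths are not modelled.

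With full follow-up, 24-week PFS is 0.5^(24/16) = 35.4%, and the Kaplan-Meier median falls on the week-18 scan. Simulated values (1,000,000 subjects per row), with the difference from 35.4% in brackets:

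| Share stopping | None has a scan showing PD | Half have a scan showing PD |
|---|---|---|
| 10% | 38.4% (+3.0) | 36.6% (+1.2) |
| 20% | 41.9% (+6.5) | 38.0% (+2.6) |
| 30% | 45.9% (+10.5) | 39.4% (+4.0) |
| 40% | 50.4% (+15.0) | 41.1% (+5.7) |

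The median moves in scan-interval steps. With no scans at stopping it stays at week 18 for 10%, is week 24 for 20% and 30%, and sits on the boundary between weeks 24 and 36 for 40%. With half scanned it stays at week 18 up to 30%.

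**Second model, different assumptions.** Medians of 3.3, 4.4 and 6.7 months (values among those quoted in Section 1.2.1), 10-30% stopping at progression, and the end-of-treatment scan done only when the last scan was more than 6 weeks old, detecting either none or all progressions. Change in 6-month PFS against scanning to progression:

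- censored at the last scan: +2.7 to +11.6 points;
- later death counted as the event (assumed median 6 months after stopping): +2.6 to +13.9 points;
- clinical progression counted as an event: -0.1 to -0.5 points.

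With censoring at the last scan, the median did not change at 10-20%. At 30% it rose only when the end-of-treatment scan detected nothing.

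DOR was not simulated; its direction follows from its definition.

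**The case against.** **Existing scans narrow the gap.** A reader might infer that these subjects get no further scan at all. The documents do not support that. The end-of-treatment scan is required when the last one is more than 6 weeks old, and Section 6.1.3.5 permits unscheduled scans when progression is suspected, which fits clinical deterioration. This stands, and it is why the right-hand column is shown. It does not close the gap: the waiver covers most stops before week 24, and unscheduled scans are optional.

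**Censoring is not fixed.** A reader might also infer that the plan censors these subjects for PFS. Section 11.4 leaves that to the SAP, death is a PFS event, and survival follow-up continues. This stands as a limit on the mechanism, but a late death still lengthens PFS. For DOR as defined in 7.1.1, death is not an event, so the point is firmer.

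**The two rules may agree in part.** The condition in 17.2.2.4.5 about remaining on study is ambiguous, because 5.6.1 describes stopping for PD, clinical progression or an adverse event as withdrawal from the study. On that reading 17.2.2.4.5 need not conflict with 7.1.1. The sentence in 17.2.2.4.4 still conflicts for exactly the subjects at issue. Dose Expansion procedures are redacted, so imaging after treatment there cannot be judged.

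**The stakes are modest.** With 18 subjects, the standard error of a 35% rate is sqrt(0.35 x 0.65 / 18), about 11 points, as large as most of the illustrated shifts. The RDE rests on safety, PK, biomarker and tumor response data (Section 3.2.1.6), not on PFS or DOR. This stands. It bears on priority; a systematic error is not removed by being smaller than random error.

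**Conclusion.** The concern holds in limited form. Section 7.1.1 conflicts with 17.2.2.4.4 for subjects who stop with clinical deterioration, and arguably with 17.2.2.4.5. Following 7.1.1 leaves PD unobserved for many of them and biases Kaplan-Meier PFS and DOR upward.

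The direction follows from the endpoint definitions; the amount does not. The range of about 1 to 15 points in 24-week PFS rests on an assumed 16-week median, an assumed 10-40% share and an assumed frequency of scans at stopping. A reader might infer a definite shift in median PFS, for example from week 18 to week 24. The documents do not support one: the median may not move at all.

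This is a worthwhile correction to descriptive secondary endpoints. It touches no sample size, error rate or dose decision.

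**What to change.** 1. **Protocol.** Reconcile Sections 7.1.1, 6.1.3.8, 6.1.3.10, Table 6.2 and 17.2.2.4. Subjects who stop without PD should stay on the existing scan schedule until PD, start of new anticancer therapy, death, withdrawal of consent or loss to follow-up. Changing 7.1.1 alone would leave the visit sections and Table 6.2 without imaging after the end-of-treatment visit. Replace or define the on-study condition in 17.2.2.4.5.
2. **SAP, main analysis.** State the censoring rules for PFS and DOR, including discontinuation without PD and the start of new anticancer therapy.
3. **SAP, sensitivity analysis.** Repeat PFS, with a matching analysis for DOR, counting discontinuation for clinical progression as an event. In the second model this nearly removed the PFS bias. It uses the discontinuation reason that Section 5.6.1 already requires to be recorded.

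**Cost:** protocol wording, a few post-treatment scans already implied by 17.2.2.4.5, and one more analysis for each endpoint. Ending scans at new therapy leaves some progressions unobserved. Information on later therapy is collected only where available, so step 3 should not depend on it.

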8. PHARMACOKINETIC/PHARMACODYNAMIC ASSESSMENTS

8.1. Pharmacokinetic (PK) Assessment(s)

Blood samples for PK analyses of DS-1205a and gefitinib should be obtained at the time points specified in the Schedule of Events ([Table 6.1](#), [Table 6.2](#), and [Table 6.3](#)).

Sampling time points may be modified based on available data from PK analyses during the study. At each time point, a 3-mL blood sample will be collected for DS-1205a and/or gefitinib analysis. If both DS-1205a and gefitinib are measured at the same time point, separate 3-mL samples should be obtained. Instructions for the collection, handling, storing and shipping of the PK samples for DS-1205a and gefitinib PK analyses will be included in the Laboratory Manual. The actual date and exact time of study drug administration and of blood sampling for DS-1205a and gefitinib PK analysis must be recorded on the eCRF.

All PK samples should be taken at as the exact nominal time point as possible. If time points of PK sampling coincide with those of Safety or Endpoint ECG, PK samples should be taken immediately after ECG measurement.

Plasma concentrations of study drugs will be measured using validated assays at Sponsor-designated bioanalytical laboratories. The samples may be used for bioanalytical method development and validation. The leftover PK samples after bioanalysis will be used for metabolite profiling, and the results will be reported separately.

Plasma concentrations will be used to determine the following PK parameters using the actual sample collection times and the standard non-compartmental analysis (NCA).

- Cmax, Tmax, Ctrough, AUCtau, and other PK parameters as appropriate.

